mesylate resulted in increased flow but a much more pronounced effect was seen with pentoxifylline.³² Interestingly, the pentoxifylline treated group showed preferential improvement in flow among the more ischemic brain tissue, and patients reported improvements in sleep disturbances, vertigo, and tinnitus.³² The selective improvement in flow among areas that are relatively ischemic is felt to be associated with the hemorrheologic mechanism of pentoxifylline and is proposed to be unique to drugs that work in this way without such beneficial effects in other medications such as vasodilators.³² While these reports suggest that pentoxifylline use is beneficial, small numbers of patients were included and non-validated instruments were used to measure symptomatic improvement. Therefore, further investigation into the efficacy of pentoxifylline for treatment of imbalance due to vascular etiologies is necessary, including identification of particular subsets of patients most likely to benefit from treatment. Many trials in varied populations demonstrate that pentoxifylline has an excellent safety profile with minimal increase in adverse effects over placebo making it an ideal agent to study and use if efficacy is demonstrated.^{29,30,32}

Project design and Procedures:

Adults, 18 years of age and over, presenting to the University of Missouri Department of Otolaryngology Head and Neck Surgery with chief concern of vertigo, dizziness, or imbalance will be considered for study. All individuals will undergo comprehensive clinical evaluation including otoscopic examination and testing of cerebellar function, gait observation, and dix hallpike maneuver. Additionally, all individuals will receive an audiogram and complete preintervention balance questionnaires, per standard of care. MRI of the brain/internal auditory canal as well as formal vestibular function testing will be conducted at the discretion of the enrolling provider. Individuals diagnosed with multisensory losses, presbystasis, bilateral

vestibulopathy, central vascular insufficiency, small vessel circulatory disease, generalized imbalance, and idiopathic peripheral vertigo scoring at least 16 on the Dizziness Handicap Inventory will be offered participation in the study. Patients must have sufficient English skills to complete the required surveys.

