Potential participants will be excluded if any of the following diagnoses are made: benign paroxysmal positional vertigo, Ménière's disease, vestibular migraine with headache, intracranial mass, perilymphatic fistula, or multiple sclerosis. In addition, individuals will be ineligible if there is history of cholesteatoma, prior ear surgery other than myringotomy and tube placement, prior radiation therapy to the head and neck, or previous use of vestibulotoxic medications where the enrolling provider determines the drug exposure to be the cause of imbalance. Use of blood thinning medications or intolerance/allergy to pentoyifylline or methylxanthines, as well as recent cerebral or retinal hemorrhage (past 3 months), will result in exclusion. Females must not be pregnant or lactating and individuals must use adequate contraception during the study period. Females of child bearing potential will be administered a pregnancy test prior to starting the study medication.. Use of any other medications to control vertiginous symptoms and participation in vestibular rehabilitation during the study period will be prohibited.

Patients electing to participate will be randomized to receive either 400 mg of pentoxifylline three times daily for 12 weeks or placebo three times daily for 12 weeks. Allocation will be made randomly and providers and patients blinded to treatment arm. Study medications will be provided to participants at no cost, and plant cellulose will be used as placebo. Outcomes will be measured in three domains: quality of life (handicap), symptom severity, and functionality. Data will be obtained prior to initiation of therapy and at designated time intervals into treatment: 4-6 weeks and 12-14 weeks (Figure 1).

The Dizziness Handicap
Inventory will be used to assess
quality of life, the European
Evaluation of Vertigo for symptom
severity, and the Vestibular
Activities and Participation
Measure to assess functionality.
Patients will be asked to report the
number of falls in the preceding 3
months as well as document any

All patients presenting to University of Missouri Department of Otolaryngology Head and Neck Surgery with imbalance, dizziness, or vertigo will be screened according to inclusion/exclusion criteria.

All individuals meeting inclusion criteria without exclusion will be offered participation.

Patients will be randomly allocated into the active treatment or placebo group in double blind fashion.

70 "Placebo"

70 "Pentoxifylline"

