4-6 weeks following treatment, patients will be reassessed. Three validated questionnaires will be completed, missed days of work tabulated, and falls recorded. Adverse effects will be documented. The assigned treatment will be continued. If inadequately tolerated dose will be reduced to twice daily.

12-14 weeks following treatment, patients will be blindly reassessed. Three validated questionnaires will be completed, missed days of work tabulated, and falls recorded. Adverse effects will be documented. Allocation will be revealed and patients will be offered to start/continue treatment with the active agent.

Figure 1: Study Design

falls during the study period. Finally, participants will be queried regarding their working status and the number of missed days due to vertiginous symptoms in the past three months prior to participation and during the study period. Head or neck imaging and vestibular function study results will be assessed by chart review at the conclusion of the study. The following adverse effects will be recorded at each clinic visit: angina/chest pain, arrhythmia/palpitation; flushing; abdominal discomfort; belching/flatus/bloating; diarrhea; dyspepsia; nausea; vomiting; agitation/nervousness; dizziness; drowsiness; headache; insomnia; tremor; blurred vision.

Medical comorbidities will be reviewed to facilitate subgroup analysis. Determination of treatment effect will be made through implementation of ANOVA testing, through IBM SPSS Statistics software.

Based upon reported data for improvement with pentoxifylline and placebo effect, at an alpha level of 0.05 and beta of 0.2, a power of 80% can be reached with 70 patients per treatment group (140 patients total).³³ We will enroll an extra 20 patients to patient dropout for a total of

160 patients to be enrolled. According to present clinic patterns, we anticipate target enrollment will be reached in approximately 18 months.

Data Handling

All data will be collected both in hard copy and electronic formats. Hard copy data will be stored in a locked office in a locked filing cabinet. Electronic data will be stored on a secure MU network drive that is encrypted and password protected. The research coordinator is responsible for access to both of these locations. Additionally, consents are signed electronically and stored on the secure network drive.

Significance of Research to the Specific Field and Stature of the University:

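### The efficacy test is given only as ANOVA, with no response form, visit or baseline covariate tied to it; if run on final or change scores, it will generally be less precise than ANCOVA on baseline scores already collected

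*Combined protocol and SAP*

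**What the plan says.** The analysis text is in Project design and Procedures, after Figure 1. The treatment effect is covered by one sentence: "Determination of treatment effect will be made through implementation of ANOVA testing, through IBM SPSS Statistics software". No ANCOVA, covariate or baseline adjustment is mentioned anywhere.

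The same section defines the outcomes and the visits:

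- Outcomes: "Outcomes will be measured in three domains: quality of life (handicap), symptom severity, and functionality". One questionnaire is named for each domain.
- Timing: "Data will be obtained prior to initiation of therapy and at designated time intervals into treatment: 4-6 weeks and 12-14 weeks".
- Before treatment, all individuals "complete preintervention balance questionnaires, per standard of care".
- At the end, in Figure 1: "12-14 weeks following treatment, patients will be blindly reassessed. Three validated questionnaires will be completed".
- Entry requires "scoring at least 16 on the Dizziness Handicap Inventory".

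So instruments and visits are named, but none is tied to the ANOVA.

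On sample size, the plan states that "at an alpha level of 0.05 and beta of 0.2, a power of 80% can be reached with 70 patients per treatment group". The basis given is "Based upon reported data for improvement with pentoxifylline and placebo effect", with no outcome, difference, SD or rate.

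**The concern.** The one sentence allows several analyses of the same questionnaire, and they differ in precision. Two simple readings are a comparison of 12-14 week scores and a comparison of changes from baseline. The first makes no use of the baseline score. The second subtracts it in full, whatever the correlation. ANCOVA estimates from the data how much of the baseline to remove.

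What is at stake is efficiency. Under randomisation all three analyses are valid, so there is no bias. But on either simple reading, the confidence interval for the treatment effect would generally be wider than the collected data allow. Which simple reading is worse depends on r, which the documents do not give: final scores when r is above 0.5, change scores when r is below 0.5 (equal SDs).

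**Working it through.** **Inputs from the plan.** 70 per arm, alpha 0.05, power 80%; questionnaires at baseline, 4-6 weeks and 12-14 weeks; an entry score of at least 16 on the Dizziness Handicap Inventory.

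**Assumed inputs.** The correlation r between baseline and 12-14 week score, taken as 0.3 / 0.5 / 0.7. Equal SDs at the two times, relaxed below.

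**The plan's own figure.** The 70 per arm cannot be reproduced, because no effect size or SD is given. Solving backwards (two-sided, normal approximation), it corresponds to a standardised difference of (1.960 + 0.842) × √(2/70) = 0.474. The results below do not use this value.

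**Variance factors**, in units of the final-score variance:

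- Final score: 1
- Change score: 2(1 − r)
- ANCOVA: (1 − r²) × (1 + 1/136), where the second term is the cost of estimating the slope with 70 per arm

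The reduction in standard error (SE) is 1 − √(ratio of factors). The equivalent n per arm is 70 divided by that ratio.

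| | r = 0.3 | r = 0.5 | r = 0.7 |
|---|---|---|---|
| ANCOVA factor before slope cost | 0.91 | 0.75 | 0.51 |
| Change-score factor | 1.40 | 1.00 | 0.60 |
| SE reduction against final score, before / after slope cost | 4.6 / 4.3% | 13.4 / 13.1% | 28.6 / 28.3% |
| SE reduction against change score, before / after slope cost | 19.4 / 19.1% | 13.4 / 13.1% | 7.8 / 7.5% |
| Final-score n per arm matching ANCOVA with 70 | 76 | 93 | 136 |
| Change-score n per arm matching ANCOVA with 70 | 107 | 93 | 82 |

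A simulation of 40,000 trials per r with 70 per arm agrees. At r = 0.5 the SEs for final, change and ANCOVA were 0.1685, 0.1687 and 0.1463, and 1 − 0.1463/0.1685 = 13.2%.

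**Unequal SDs.** Let k be the final-to-baseline SD ratio. The change-score factor becomes 1 + 1/k² − 2r/k. Before the slope cost it exceeds the ANCOVA factor by (r − 1/k)², which is never negative. After the slope cost, the SE reductions against change scores at r = 0.3 / 0.5 / 0.7 are 28.9 / 24.1 / 20.5% for k = 0.8 and 11.1 / 5.2 / 0.6% for k = 1.25.

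**Where the gain disappears.** Against final scores, break-even is at r = √(1/137) = 0.085. At r = 0 the ANCOVA SE is √(1 + 1/136) − 1 = 0.4% larger. Against change scores, the same 0.4% loss occurs at r = 1/k, for example r = 0.8 when k = 1.25.

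**The entry cut-off.** Selecting on baseline narrows its SD, which lowers r and raises k for the Dizziness Handicap Inventory. Assume the cut-off removes the lowest 10% or 30% of a normal baseline distribution. The baseline SD is then multiplied by s = 0.844 or 0.702. In units of the unselected variance, the final-score factor is 1 − r² + r²s², the change-score factor is (1 − r²) + (1 − r)²s², and the ANCOVA factor stays at 1 − r². SE reductions before the slope cost:

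| r before selection | Against final score, 10% / 30% removed | Against change score, 10% / 30% removed |
|---|---|---|
| 0.3 | 3.3 / 2.4% | 15.0 / 11.1% |
| 0.5 | 10.1 / 7.3% | 10.1 / 7.3% |
| 0.7 | 22.9 / 17.6% | 5.7 / 4.1% |

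In the r = 0.5 row, the correlation after selection is 0.44 or 0.38.

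**The case against.** The strongest objection is that no error in the plan is shown. The sentence on ANOVA contradicts nothing, an unadjusted ANOVA is valid in a randomised trial, and the analysis criticised is one the plan never says it will run. With scores at three times, repeated-measures ANOVA is a natural reading. A general linear model with a covariate is another, and under it the loss disappears. This stands, and it is why the precision claim is conditional on two readings.

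No general claim can be made against repeated-measures ANOVA. Its 2-df group-by-time test does not by itself estimate the 12-14 week difference, and its power relative to ANCOVA depends on r and on the effect at 4-6 weeks. With equal effects at both visits and compound symmetry, it overtakes 12-14 week ANCOVA at about r = 0.75 if 70 per arm gives 80% power on final scores, and at about r = 0.82 if it gives 80% on change scores.

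A reader might infer that the trial is underpowered or that 70 per arm is wrong. The documents do not support that: the effect size and SD behind the 70 are not stated, and the analysis it was computed for is not named. A reader might also infer that the sponsor has decided to ignore baseline. The text is silent, which is not the same thing.

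It is also fair to object that the equal-SD figures may flatter ANCOVA for the one instrument with an entry cut-off. That stands, and the second table shows the reduced gains against both comparators.

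**Conclusion.** The point holds as a conditional efficiency gain that should be taken. The plan ties no form of response, visit or baseline covariate to its efficacy test. If that test is run on final or change scores, baseline-adjusted ANCOVA is generally more precise and uses only data already collected. The direction holds across the assumed range of r. The size rests on r, the SD ratio and, for the Dizziness Handicap Inventory, the share of patients removed by the cut-off, none of which the documents give. The possible loss of about 0.4% in SE is trivial beside the likely gain. The result bears on precision only, not on bias or on the stated power.

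**What to change.** Keep the ANOVA sentence for the other outcomes, because replacing it would leave falls and missed work days without any stated test. Add after it:

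*For each questionnaire, the 12-14 week score will be compared between randomised arms by ANCOVA with the same instrument's baseline score as covariate.*

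If the sponsor also analyses the 4-6 week scores, or uses a repeated-measures model, baseline should enter as a covariate there too. The added sentence fixes the response, visit and use of baseline for the questionnaire comparison. It does not choose a primary questionnaire or settle the analysis of falls and missed work days.

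The cost is one sentence. It needs no new data, visits or patients, and the named software already offers ANCOVA.

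### Dropout is met only with 20 extra patients and ANOVA; with no analysis population, missing-data method or outcome collection after stopping drug, bias of 0 to about 0.15 SD, in either direction, is possible under assumed loss

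*Combined protocol and SAP*

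**What the plan says.** All of this is in the combined protocol and SAP, section Project design and Procedures.

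- **Size.** "Based upon reported data for improvement with pentoxifylline and placebo effect", and "at an alpha level of 0.05 and beta of 0.2", the plan states that "a power of 80% can be reached with 70 patients per treatment group (140 patients total"). No effect size, standard deviation or response rate is given.
- **Dropout.** "We will enroll an extra 20 patients to patient dropout", making "160 patients to be enrolled". Nothing else is said about patients who leave.
- **Analysis.** "Determination of treatment effect will be made through implementation of ANOVA testing, through IBM SPSS Statistics software". No analysis population, covariate, missing-data rule or sensitivity analysis is named.
- **Visits.** The three questionnaires are completed before treatment, at 4-6 weeks and at 12-14 weeks.
- **Restrictions.** "Use of any other medications to control vertiginous symptoms and participation in vestibular rehabilitation during the study period will be prohibited". The plan does not say whether a patient who breaks this rule, or who stops study drug, is still followed and analysed.

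**The concern.** Adding patients restores the number analysed but not the randomised comparison. If the patients who leave differ in prognosis from those who stay, and differ in another way or to another degree in the other arm, a comparison of those who stay is biased however many were enrolled.

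The plan gives some reason to expect this. It lists 16 adverse effects to record and allows for poor tolerance, and it bars other vertigo treatment, which gives an unrelieved patient a reason to leave. The main outcomes are self-reported questionnaires. At stake are a benefit that does not exist, or a real one that is hidden. The 4-6 week scores carry information on patients lost later, and the plan makes no stated use of them for that purpose.

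**Working it through.** **1. The plan's own figures.** The dropout step reproduces: 20/160 = 12.5%, and 140/(1 − 0.125) = 160. With equal allocation that is 80 randomised and 70 remaining per arm. The 70 itself cannot be reproduced, because no effect size is stated. Solved backwards (two-sided 5%, 80% power), SE = √(2/70) = 0.169 SD, and (1.960 + 0.842) × 0.169 = 0.474 SD; with the t distribution it is about 0.477 SD.

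**2. Whom ANOVA would use.** Without imputation, ANOVA on the final score needs a 12-14 week value, and the classical repeated-measures form needs every visit. The sizing fits this: 140 analysed out of 160 enrolled.

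**3. Bias among those who remain.** Let d be the fraction lost per arm and g the amount by which dropouts score worse than their full-arm mean, in SD. The mean of those remaining moves by −g × d/(1 − d). At d = 0.125 the multiplier is 0.125/0.875 = 1/7. The bias in favour of the drug is therefore (g active − g placebo)/7. Rejection with no true effect is 1 − Φ(1.96 − b/0.169) + Φ(−1.96 − b/0.169). The values of g are assumptions.

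| g active | g placebo | Bias b (SD) | Rejection |
|---|---|---|---|
| 0.5 | 0.5 | 0 | 5.0% |
| 0.5 | 0 | 0.071 | 7.1% |
| 0.8 | 0 | 0.114 | 10.4% |
| 1.0 | 0 | 0.143 | 13.5% |
| 0.5 | −0.5 | 0.143 | 13.5% |

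Exchanging the arms reverses the sign of the bias. A bias of exactly 0.15 SD gives 14.4%, and needs g to differ between arms by 0.15 × 7 = 1.05 SD.

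**4. Simulation check.** Settings: 80 per arm, 10 lost per arm, correlations of 0.6 (baseline with 4-6 weeks), 0.5 (baseline with 12-14 weeks) and 0.7 (4-6 with 12-14 weeks), all assumed. Loss depends on the 4-6 week score plus noise. Strong selection in one arm gave 0.14-0.15 SD and 14.5-16% rejection; moderate gave 0.11 SD and about 11%; mild gave 0.07-0.08 SD and about 7%. If exactly the ten worst-scoring patients in one arm leave, the bias is 0.163 SD, the ceiling for one-arm selection on that score. Strong selection in opposite directions gave 0.30 SD and 46%.

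**5. Power.** True effect 0.477 SD, with placebo dropouts 1 SD worse than their arm and active losses random: 0.477 − 0.143 = 0.334; 0.334/0.169 = 1.976; power = Φ(1.976 − 1.960) = 51%, against about 80% with random loss. With placebo dropouts 0.5 SD worse: (0.477 − 0.071)/0.169 = 2.402, and power = Φ(0.442) = 67%.

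**6. What other analyses recover.** Under strong one-arm selection, adjusting only for baseline among those remaining left 0.08-0.09 SD of bias. Using the 4-6 week score as well left about 0, but only because loss was simulated to depend on that score. When loss depended on the unseen 12-14 week score, about 0.08-0.12 SD remained.

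**The case against.** **The plan never says it analyses completers.** A reader might infer that it chose to. It did not: it is silent, and Figure 1 has allocated patients reassessed at both visits with no withdrawal rule. This stands. The defect is an unspecified population together with a test that falls back on available final scores. Silence still leaves the choice until the data have been seen.

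**The large figures are assumed scenarios.** A reader might infer that dropout will triple the false-positive rate. The documents give no dropout rate by arm and nothing on how dropouts fare. Loss in one arm with odds ratios of 1.35 to 2.0 per SD of outcome gives only 0.035-0.083 SD and 5.3-8.0% rejection. This stands, so only a range can be given.

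**The direction may not favour the drug.** A reader might infer a spurious benefit. Side effects on active drug and lack of relief on placebo mainly imply bias against pentoxifylline. With the worst placebo patients leaving and no true effect, rejection was 14.7%, but only 0.2% of trials favoured the drug. A false benefit needs the worst-scoring active patients to leave while placebo losses are unrelated to outcome, and nothing in the documents points to that in particular. This stands too.

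**Differential loss may be small.** The section Preliminary work/results expects little excess of adverse effects over placebo. The plan provides a response to poor tolerance short of withdrawal. Patients are blinded, and all are offered the active agent after the last visit, which is a reason to stay. These provisions lower the risk but do not remove it.

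**Conclusion.** The concern holds as a gap in the plan combined with an analysis that has a better alternative using visits already scheduled. Extra enrolment deals with the count and leaves selection unaddressed. The bias could be nothing, or about 0.15 SD either way under strong selection in one arm; selection in opposite directions could give more. For scale, 0.15 SD is about a third of the 0.474 SD that the sample size can detect (0.15/0.474 = 0.32).

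These sizes rest on assumed loss of 12.5% in each arm, a two-sided test (the plan does not state sidedness), assumed visit correlations and assumed differences between dropouts and those who stay. That the gap exists rests on none of these. The documents do not support saying that the plan selected a completer analysis, that a false benefit is the likely result, or that a mixed model would remove all bias.

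**What to change.** 1. State that the primary analysis includes all randomised patients in the arm assigned, whatever study drug they took and whether or not they used prohibited treatment.
2. Replace ANOVA with a likelihood-based repeated-measures model, for example SPSS MIXED, on the 4-6 and 12-14 week scores, with arm, visit, arm-by-visit and baseline score, and read the effect at 12-14 weeks. Other methods, such as multiple imputation using the 4-6 week score, would also serve.
3. State that stopping study drug is not leaving the study, and keep collecting the three questionnaires from those patients, by mail or telephone if needed. These data cannot be recovered later, and they are the only protection for patients lost before 4-6 weeks, who have no intermediate score.
4. Add one sensitivity analysis for data missing not at random, such as delta-adjusted multiple imputation, because the model removes bias only when dropout depends on observed scores. Report loss and its reasons by arm, and show patients with complete data as supportive only.

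The cost is a paragraph of analysis text, a slightly more complex procedure in software already named, and follow-up contact with about 20 patients. The estimate will include patients who stopped drug and may be somewhat smaller.
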